13.2 Randomization

Upon documented and confirmed eligibility, the patient will be enrolled and randomized. Randomization for phase II portions of the study will be done through [name] and colleagues in the biostatistics core at the University of Chicago in a 1:1 fashion. There will be no specific stratification as the 12-week standard of care enzalutamide lead in for the phase II study we hypothesize will add homogeneity to the population. As only patients with stable disease or better at 12 weeks are randomized any affect of prior therapy, etc. on the study population will be mitigated.

13.3 Analysis of Secondary Endpoints

The stratified log-rank will be used to compare the two treatment arms with respect to progression-free survival (PFS). PFS is defined above. For patients without disease progression at the time of analysis, PFS will be censored at the time of the patient's last tumor assessment. The Kaplan-Meier approach will be used to estimate PFS distribution and the proportional hazards model will be used to assess the importance of treatment arm in predicting PFS.

The pharmacokinetic data will be obtained from PK samples described above (Section 7.2.1.). These PK parameters will be summarized using standard descriptive methods (means, standard deviations, medians and ranges).

The primary objective of the exploratory CTC aim is to assess intra- and inter-patient variability in AR and GR expression within CTCs from patients with progressive CRPC. The second objective of this aim is to explore the correlation between baseline AR and GR expression and PSA progression-free survival in patients treated with enzalutamide ± mifepristone. The median/range, mean/standard deviation of expression (relative fluorescence) for AR and GR will be summarized for each patient (intra-patient variability) and for the entire population (inter-patient variability). The components of variability will be estimated using analysis of variance. In addition percent nuclear/cytoplasmic/both cellular localization will be calculated for both receptors. Finally, Cox regression models for time to PSA progression will be fit using the expression of AR and GR as covariates incorporating treatment-by-marker interaction terms to determine whether they have prognostic and/or predictive value. Based on prior studies in this patient population ~50-60% of patients enrolled will have CTCs isolated and available for imaging. The percentage of patients with CTC's following 12 weeks of enzalutamide is unknown, but likely lower, and thus we will assume 30% will have evaluable CTC's at the time of randomization. This should provide ~25 patients (.3x82) for analyses.

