5.3 Phase II Study Drug Administration (Figure 4)

- Eligible subjects will be enrolled and registered within the first 12 weeks of standard of care enzalutamide 160mg/day for CRPC and randomized to one of the following two arms:
 - Arm 1: Enzalutamide 160mg/day standard dose
 - Arm 2: Enzalutamide + Mifepristone at RP2D
- Subjects will begin randomized study treatment after 12 weeks of standard of care enzalutamide lead-in. Treatment on study may start up to 14 weeks after initial enzalutamide (+2 week grace period).

Figure 4: Phase II Enrollment and Study Treatment timeline

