11.4 Progression-Free Survival

Progression-free survival (PFS) is defined as the duration of time from start of treatment to time of progression (by either PSA or RECIST) or death, whichever occurs first.

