13.0 STATISTICAL CONSIDERATIONS

13.1 Sample Size/Primary Endpoint

Within the phase I portion of the study, steady-state C_{trough} for Enzalutamide and the active metabolite will be determined for each patient and means and standard deviations calculated. As described above, the mean of the ratio of C_{trough} for Enzalutamide and the active metabolite will be calculated for each dosing cohort, and mean value will be used for dos adjustment determinations. Standard deviation and range of the C_{trough} and ratio will also be calculated and reported.

The randomized phase II study, will be conducted with appropriate sample size to power primary endpoint- to determine if mifepristone in combination with enzalutamide prolongs time to PSA progression compared to enzalutamide alone in patients with metastatic castration resistant prostate cancer. The primary statistical consideration will be PSA progression-free survival (PFS) post randomization, defined as the time to PSA progression or death, whichever comes first. PSA progression will be defined as a PSA (confirmed 2 weeks later) that is ≥ 1.25 times (25% increase) the PSA at randomization (week 12). We assume the median time to PSA progression in the control (enzalutamide alone) arm will be 6 months post randomization. The rationale for this assumption is as follows. In the phase III enzalutamide (AFFIRM) trial¹³, ~10% of treated patients had PSA progression prior to 12 weeks. The PSA progression-free rate was ~42% at 9 months, which would correspond to a 6-month rate, conditional on no event at 12 weeks, of $0.42/0.9=0.47$. Thus our enrichment strategy should lead to a patient population with a median PFS of 6 months (24 weeks) in the control arm post randomization. In order to detect a hazard ratio (HR) of 0.60, which corresponds to an increase in the median from 24 to 40 weeks, with 80% power, a sample

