size of 84 patients (42/arm) is required, using a one-sided test at the $\alpha=0.10$ significance level. This assumes a two-year accrual period and a subsequent one-year follow-up period. Kaplan-Meier⁴¹ curves will be generated and the two treatment arms compared using a logrank test. Median time to event in each group will be estimated along with 90% confidence intervals using the method of Brookmeyer and Crowley⁴². Cox⁴³ proportional hazards regression models will be fit to assess and adjust for the effects of baseline covariates. Overall survival and radiographic progression-free survival will be analyzed similarly. The relative PSA change within each arm will also be reported using a waterfall plot according to working group recommendations for phase II studies in CRPC, as a secondary endpoint⁴⁴. Adverse events will be summarized by grade and type and compared between groups using chi-square or Fisher's exact tests.

For the secondary endocrine PD endpoint, we will compare endocrine PD marker differences between the enzalutamide alone versus the Enzalutamide + Mif treatment arms. In previous placebo controlled trials of Mif, serum cortisol levels reliably doubled from a baseline of approximately 15 $\mu\text{g}/\text{dL}$ to $>30 \mu\text{g}/\text{dL}$ after treatment with mifepristone^{38,39}. Based on the reported interquartile ranges, and assuming normality of the distribution, the coefficient of variation is estimated at 50%. An interim futility analysis will be conducted after half (35) of the expected 70 PSA events are observed. At this stage we will conduct an interim analysis of the difference in cortisol levels; a lack of biomarker effect would provide justification for closing the trial. Thus, assuming a true mean for the control arm of 15 and standard deviation of 7.5 on day 29 post randomization, our sample size will provide 90% power to detect a difference of 15 vs. 22 $\mu\text{g}/\text{dL}$ between the two treatment arms, based on t-test at a two-sided alpha level of 0.05. This calculation allows for a 15% missing data rate prior to day 29 post randomization. The other endocrine laboratories collected at day 29, will be similarly compared between treatment groups.

In addition, if at the interim analysis the conditional power for the primary PSA endpoint is $<25\%$, we will consider terminating the trial for futility. This stopping rule will provide minimal power loss ($<3\%$)⁴⁴.

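### Section 13.3 names a stratified log-rank without strata, and the radiographic PFS and OS comparisons of 13.1 rest on data that stop when a patient leaves the study

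*Combined protocol and SAP*

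**What the plan says.** **Test.** For the secondary endpoint, 13.3 says: "The stratified log-rank will be used to compare the two treatment arms with respect to progression-free survival (PFS"). Section 13.2 says: "There will be no specific stratification". For the primary endpoint, 13.1 has "the two treatment arms compared using a logrank test", with no mention of strata.

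**PFS definition.** Section 13.3 adds only that "PFS is defined above" and censors patients without progression at the last tumor assessment. Two definitions come before it. Section 11.4 gives the "duration of time from start of treatment to time of progression (by either PSA or RECIST) or death". Section 13.1 gives "PSA progression-free survival (PFS) post randomization, defined as the time to PSA progression or death, whichever comes first".

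**Origins.** Section 13.1 measures PSA progression against "the PSA at randomization (week 12"), whereas under 5.3 "Treatment on study may start up to 14 weeks after initial enzalutamide".

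**Radiographic PFS and OS.** Section 2.2 lists radiographic and clinical progression-free survival as a secondary objective. OS is in neither 2.1 nor 2.2. The only analysis text for radiographic PFS and OS is one sentence in 13.1 saying that they are handled in the same way as the primary endpoint.

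**Observation.** Section 6.0 ends therapy at working-group progression, cites Appendices C and D, and notes when PSA progression is first assessed. Imaging is every 12 weeks while on study (7.2). Assessments end when the patient is taken off study, with one further scan unless a recent one exists (7.3). The calendar's last visit falls within 30 days of the last enzalutamide dose. Adverse events are recorded to 30 days after the last dose (10.1).

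**The concern.** The stratified wording leaves the programmer to choose strata, or to ignore the word, in an open-label trial. The PFS tested in 13.3 mixes PSA with RECIST progression, so it cannot show whether mifepristone delays radiographic progression.

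The larger problem is in the data. If PSA progression takes a patient off study, radiographic progression and death after that point are mostly not captured. Radiographic PFS is then censored by an event that the trial expects to differ by arm. If PSA and radiographic progression are correlated, that censoring is informative. A null radiographic result could be read as no effect when many events were never observed, and a result called overall survival would describe only deaths on study or soon after.

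**Working it through.** **1. The plan's own figure.** Inputs from 13.1: HR 0.60, 80% power, one-sided alpha 0.10, 84 patients, 24 months of accrual plus 12 of follow-up, medians 24 and 40 weeks (about 6 and 10 months).

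- Events (Schoenfeld) = 4(1.2816 + 0.8416)² / (ln 0.60)² = 69.1, rounded up to 70. This matches the 70 expected events in 13.1.
- Event probability with uniform accrual A and follow-up F: 1 − [exp(−λF) − exp(−λ(A+F))]/(λA). It is 0.915 for a 6-month and 0.788 for a 10-month median.
- Expected events: 42 × (0.915 + 0.788) ≈ 71.5, with power 0.81.

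The primary design reproduces without strata. The documents give no figure for radiographic PFS or OS, so everything below is illustration.

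**2. Events left if observation stops at PSA progression, assuming independence.** With L = λr + λp, the chance of seeing the event is (λr/L) × {1 − [exp(−LF) − exp(−L(A+F))]/(LA)}. Here λr is the hazard of the secondary event (same in both arms) and λp the PSA hazard (medians 6 and 10 months).

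Example, radiographic median 12 months: 0.323 (control) and 0.424 (combination), so 42 × 0.747 = 31.4 events, against 84 × 0.729 = 61.3 with full follow-up.

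| Endpoint | Assumed median (months) | Full follow-up | To PSA progression | Kept |
|---|---|---|---|---|
| Radiographic | 8.3 | 70.7 | 39.3 | 56% |
| Radiographic | 12 | 61.3 | 31.4 | 51% |
| Radiographic | 18 | 49.5 | 23.6 | 48% |
| Death | 15 | 54.8 | 26.9 | 49% |
| Death | 18 | 49.5 | 23.6 | 48% |
| Death | 24 | 41.2 | 18.9 | 46% |

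**3. Adding correlation and the scan schedule.** Simulation: 42 per arm, exponential times, Gaussian copula between PSA exit and radiographic progression, no PSA exit before week 12, scans every 12 weeks plus one at exit, one-sided log-rank at 0.10. Assumed: control radiographic median 36 weeks, radiographic HR 0.60, PSA-exit HR 0.60.

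| PSA-exit medians (weeks) | Correlation | Events | Power |
|---|---|---|---|
| No exit | – | 62.1 | 0.76-0.77 |
| 24/40 | 0 | 33.6 | 0.61 |
| 24/40 | 0.4 | 32.2 | 0.56 |
| 24/40 | 0.8 | 27.9 | 0.50 |
| 36/60 | 0 to 0.8 | 39.7 to 38.6 | 0.65 to 0.61 |

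Repeat simulations of the 24/40 case put power between 50% and 66%. The 36/60 rows allow for later exit, because Appendix C asks for more than the 13.1 event (for example, 50% above nadir after a PSA response). With continuous detection and no week-12 hold, the 24/40 case gives 32.1 to 22.0 events and power 0.55 to 0.39.

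**4. Direction of bias with no true radiographic effect (HR 1.0, exit 24/40).** For correlation 0, 0.4 and 0.8, one-sided false positives are about 12.7%, 9.0% and 3.6% (nominal 10%), with estimated HR 0.95, 1.02 and 1.22. Now add an assumed toxicity exit in the combination arm: 20% by week 24, correlated 0.4 or 0.8 with radiographic time. False positives rise to roughly 12-17% when the PSA correlation is zero or moderate, with 19% the highest seen. They are about 6% when the PSA correlation is 0.8.

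**5. Deaths.** Section 1.4 says only that OS is under 1.5 years. With an assumed median of 78 weeks and capture to exit plus 30 days, 49.5 deaths occur by cut-off. About 18-30 are captured if only PSA ends observation, and about 15-24 if PSA or radiographic progression does.

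**The case against.** **The stratified wording is a slip.** With no strata, the test reduces to the log-rank of 13.1. This is fair: it is an editorial error with an obvious repair, and it should not be described as making the analysis impossible.

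**PFS is defined.** Section 11.4 is the only section with that title, and censoring at the last tumor assessment fits it better than the PSA endpoint. It is the natural referent. Likewise, treating radiographic PFS in the same way as the primary endpoint plausibly carries over randomization as origin and death as an event. What remains is that neither is written for radiographic PFS and that no censoring rule is given. The gap between the two origins is at most about two weeks.

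**The bone-lesion rules conflict.** A reader might infer this from the two-lesion rule in 11.2 and the one-or-more wording in Appendix D. The documents do not support a firm contradiction, because 11.2 expressly governs bone scans and Appendix D is general RECIST text.

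**The bias must run against mifepristone, so a positive radiographic result is safe.** A reader might infer this from PSA exit alone. The plan does not support it: 6.0 also ends therapy for toxicity, withdrawal and investigator discretion, and 9.3 discontinues patients after a 28-day hold. Exits that fall mainly on one arm can favour the combination.

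**These are unpowered secondary endpoints.** True, and it limits the severity. But 13.1 still commits to comparing them.

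**Conclusion.** The point holds as a moderate one that should be fixed. From the text alone: 13.3 names a stratified test without strata; the 11.4 PFS counts PSA and does not answer the radiographic objective; radiographic PFS has no censoring rule, and its origin and the counting of death are only implied. OS is compared without being an objective and without scheduled survival follow-up.

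The main consequence is truncation at exit. It rests on the natural reading of 6.0 that PSA progression ends treatment. Across the assumed medians in the independence calculation, about half of the radiographic events and deaths remain. In the correlated illustration, power for radiographic HR 0.60 falls from about 77% to 50-66%. These sizes depend on assumed radiographic and survival medians, an assumed correlation, and the 24/40-week medians standing in for PSA exit.

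The bias can go either way: against the combination under PSA exit with strong correlation (null HR about 1.2, false positives about 4%), or towards it with zero correlation or a combination-arm toxicity exit (about 12-17%). The primary analysis and its sample size are unaffected. The undefined clinical progression in 2.2 is minor.

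**What to change.** (a) In 13.3, replace the stratified log-rank with the unstratified log-rank of 13.1. Cite 11.4 as the PFS meant and state its origin.

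(b) In 13.1, define radiographic PFS for analysis only: from randomization to RECIST 1.1 soft-tissue progression, bone-scan progression by the existing 11.2 rule, or death, without PSA. Censor at the last evaluable scan, or at randomization if there is none. Leave Appendix D and the stopping text of 6.0 as they are, since 6.0 relies on Appendix D. If the sponsor sees a conflict between 11.2 and Appendix D on new lesions, those passages must be reconciled.

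(c) Label radiographic PFS as limited to on-study observation and report it descriptively, with reasons for exit by arm. Delete the OS comparison or label it as on-study deaths only.

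These are wording changes. The price of (c) is giving up formal radiographic and OS comparisons.

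Optional instead of (c): record survival status to data cut-off and use routine-care scans after a PSA-only exit, with a stated rule for scans after new therapy and a sensitivity analysis censoring at the off-study scan. This covers up to 84 patients and may need consent or IRB changes. Those scans would be unscheduled and open label, so their timing may differ by arm.

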7.2 On Study Visits

On study visit will every 2 weeks through 8 weeks on study, then monthly. The frequency of visits early in the trial is to ensure adequate patient safety while on study.

For study visits, including day 1, the following full set of blood tests will need to be obtained: CBC, serum chemistries, LDH, PSA. In addition, as mifepristone can affect the hypothalamic-adrenal gland axis and to monitor for endocrine related adverse events, serum cortisol cortisol and thyrotropin will be assessed at day 1 and at the subsequent two monthly (day 29, 57) study visits. A second whole blood sample for circulating tumor cell correlative study will be performed on first day of study drug as described in Section 12.1. Other monthly assessments including ECOG status, concomitant medications etc. to be collected are outlined in the study calendar. To asses for potential QTc prolongation with the combination of study agents, a second EKG will be obtained after both medications at steady state. Note: monthly visits can occur ± 3 days of scheduled visit.

Disease assessment with imaging (as in pre-study evaluation) will be repeated every 12 weeks while on study, starting at first day of concomitant daily study drug administration.

7.2.1 Pharmacokinetics sampling:

Plasma samples to determine enzalutamide and M2 metabolite levels within the serum of patients on study will be collected and sent to Medivation Inc. for pharmacokinetic (PK) analysis. Patients should withhold enzalutamide administration prior to visits with PK sampling and should take enzalutamide after the PK sample is collected. The pre-dose PK sample should be taken immediately before enzalutamide administration. The PK sample should be collected even if patient did not withhold enzalutamide.

For the phase I study, the following samples will be collected for PK modeling before enzalutamide, mifepristone dose for each day. Samples will be taken weekly starting at day 29 for the next four weeks.

1. Day 29
2. Day 36
3. Day 43
4. Day 50
5. Day 57 (4 weeks after start of phase I daily concomitant dosing)

For patients in the Phase II portion of the study, PK's will be collected on day 1 of on-study period (steady-state enzalutamide alone) and after 4 weeks on study.

All samples will be shipped to:

[name], Sample Receiving
inVention Health Clinical Lab, Inc.
[name]
[name]
[contact]
[contact]
Email: [contact]

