Appendix C

PROSTATE-SPECIFIC ANTIGEN WORKING GROUP CRITERIA⁴⁹

Progressive Disease after Androgen Deprivation Eligibility Criteria:

PSA evidence for progressive prostate cancer consists of a PSA level of at least 5 ng/ml which has risen on at least 2 successive occasions, at least 2 weeks apart. If the confirmatory PSA (#3 below) value is less (i.e., #3b) than the screening PSA (#2) value, then an additional test for rising PSA (#4) will be required to document progression.

Procedures for Assessing PSA Progression Post Study Treatment

PSA measurements will be taken on a monthly basis. PSA increases and decreases will be tracked in order to assess disease response.

PSA partial response is defined by at least a 50% decline from screening (baseline) PSA value. The decline must be confirmed by a second PSA value obtained 4 or more weeks later.

PSA progressive disease may be defined in both patients who have not shown a decrease in their PSA and those who have. For patients who have not shown a decrease, progressive disease is defined as an increase of 25% over the screening (baseline) PSA value and an increase in the absolute-value PSA level by at least 5ng/mL. This increase should be confirmed by a second value.

For those patients whose PSA have decreased but has not reached response criteria, progressive disease is defined as 25% increase over the nadir PSA value provided that the increase is at least 5ng/mL and is confirmed.

Duration of PSA Response

Duration of PSA Response is measured from the time when the PSA value first declines by at least 50% of the screening (baseline) and that was eventually confirmed by a second value. It is calculated until the time at which there is an increase of 50% of PSA nadir, provided the absolute increase is at least 5 ng/mL. The increase must be confirmed by a second consecutive measurement that is at least 50% above the nadir.

If the PSA never shows a 50% increase over the nadir value, then the patient will be censored at the last PSA measurement.

Time to Disease Progression

For patients who have achieved a $\geq 50\%$ decrease from the screening (baseline) PSA, assessment of time to disease progression is when the PSA has increased 50% above the nadir and at a minimum of 5ng/mL. For patients without a PSA decrease of this magnitude or without a decrease, the time for progression is calculated at the time a 25% increase from screening (baseline) PSA has been achieved.

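### The secondary Phase II PFS rules in Sections 11.4 and 13.3 conflict on death, censoring date and time origin, and need one consistent definition

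*Combined protocol and SAP*

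**What the plan says.** Section 11.4 defines PFS as the "duration of time from start of treatment to time of progression (by either PSA or RECIST) or death, whichever occurs first".

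Section 13.3 uses PFS to compare the two treatment arms. It says only that "PFS is defined above" and then sets the censoring rule: "For patients without disease progression at the time of analysis, PFS will be censored at the time of the" last tumour assessment. It mentions neither death nor the last PSA.

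The primary endpoint in Section 13.1 is "PSA progression-free survival (PFS) post randomization, defined as the time to PSA progression or death, whichever comes first". It therefore has a different origin.

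The assessment schedules differ too. Section 7.2: "Disease assessment with imaging (as in pre-study evaluation) will be repeated every 12 weeks while on study". Appendix C: "PSA measurements will be taken on a monthly basis". Section 7.2 adds two-weekly visits with PSA through week 8.

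Section 5.3 has Phase II patients registered within their first 12 weeks of enzalutamide and randomised, with study treatment starting after week 12 and at the latest at week 14. Footnote a of the study calendar (Section 8.0) allows consent at most 28 days before study medication.

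**The concern.** Three features of the secondary PFS do not fit together.

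1. **Death.** A patient who dies without progression has a PFS event under 11.4, but is also a patient without disease progression under 13.3. An analyst who programs the 13.3 sentence as written would turn that event into a censored time.
2. **Censoring date.** A PSA rise between two scans ends PFS. A normal PSA over the same interval earns no follow-up, because the patient is censored back at the last scan.
3. **Origin.** Start of treatment is not the date of randomisation, and some patients may be randomised and never start study treatment. A comparison of randomised groups should include them.

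At stake are the event count, the reported medians and the completeness of a secondary randomised comparison. The trial is open-label, so the choice should be settled before the data are analysed.

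**Working it through.** **The plan's own figures first.** The plan gives no figures for the secondary PFS, so the primary design serves as a stand-in: HR 0.60, medians 24 and 40 weeks, one-sided alpha 0.10, 80% power, 42 per arm, two-year accrual and one-year follow-up (Section 13.1).

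- Events (Schoenfeld): 4(1.2816 + 0.8416)²/(ln 0.60)² = 69.1, so 70. This matches the plan. Power at 70 events is 0.804.
- Event probability with exponential times, uniform accrual over 104 weeks and 52 weeks of follow-up: p = 1 − (e^(−52λ) − e^(−156λ))/(104λ), with λ = ln 2/median.
- Control: λ = 0.02888, p = 0.930. Combination: λ = 0.01733, p = 0.812.
- Expected events: 42(0.930 + 0.812) = about 73. Censored: 7.0% and 18.8%, or 3.0 + 7.9 = about 11 of 84.

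**1. Deaths censored at the last scan (literal 13.3).** The documents do not give the share of first events that are deaths without progression; 5%, 10% and 20% are assumptions. The simulation used 1,500 trials, 42 per arm, a 4-week PSA grid, a 12-week scan grid, and the same HR of 0.60 for deaths and progression.

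| Assumed share | Events, deaths counted | Events, literal rule | Power, counted / literal | Control median (weeks), counted / literal |
|---|---|---|---|---|
| 5% | 72.6 | 68.9 | 0.81 / 0.80 | 25.9 / 27.3 |
| 10% | 72.7 | 65.1 | 0.81 / 0.77 | 25.7 / 28.6 |
| 20% | 72.8 | 57.5 | 0.80 / 0.74 | 25.6 / 32.3 |

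The loss is about 4, 8 and 15 events. The control median is overstated by about 1, 3 and 7 weeks.

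A closed-form check gives the direction of the hazard. Mean exposure is p/λ: 32.2 weeks in control and 46.8 in combination. For a share s, events fall by the factor (1 − s), and each censored or dead patient loses about 6 weeks. In control at s = 10%, the hazard is 0.90 × 0.930/(32.18 − 6(0.070 + 0.093)) = 0.0268 against a true 0.0289, about 7% too low. Over both arms the understatement is about 2–3%, 7% and 16% for the three shares. This already includes the opposing effect in step 2.

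**2. Last scan instead of last PSA, with deaths counted.** On a 12-week grid the mean follow-up lost up to the cut-off is about 6 weeks (6.1 in simulation).

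- Control: 32.18/(32.18 − 0.070 × 6.1) = 1.014.
- Combination: 46.85/(46.85 − 0.188 × 6.1) = 1.025.
- Effect on the hazard ratio: 0.60 × 1.025/1.014 = 0.607.

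With PSA every 4 weeks, about 2 weeks on average stay unobserved whatever the rule, so about 4 of the 6 weeks can be recovered. The recoverable part corresponds to ratios of about 1.009 and 1.016. In simulation, power changed by less than 1 point and medians by less than 1 week, including a run with added dropout (0.5% per week).

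**3. Origin.**

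- Randomisation at week 12, treatment by week 14: 14 − 12 = up to 2 weeks.
- Randomisation earlier, within the 28-day consent window: up to 28/7 = 4 weeks.
- Randomised, never treated: no start date, so no PFS time. The documents give no basis for the number of such patients.

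**The case against.** The best defence is that 11.4 governs. It names death as an event, and 13.3 refers back to a definition immediately before stating the censoring rule, so the sentence can be read as applying only to patients with no PFS event. That is probably the intent, and it is why nobody should infer that the plan will in fact drop deaths from PFS. What remains is that the only censoring rule for the endpoint, as worded, contradicts its definition. The back-reference could also be taken to mean the PSA PFS of 13.1, although 11.4 is the only general PFS definition.

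Censoring at the last tumour assessment is a recognised convention. A later PSA date credits some time during which no scan confirms freedom from radiographic progression. That objection stands for radiographic PFS, which 13.1 treats as a separate endpoint. It is weaker for a composite in which PSA alone can be the event. In addition, Section 7.3 requires imaging when a patient leaves the study unless done within four weeks, so the loss falls mainly on patients still on study at the cut-off. Adding RECIST events would also leave fewer than 11 patients censored. The ratios in step 2 are therefore upper values.

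On the origin, 11.4 also has to serve Phase I, which has no randomisation, so start of treatment is understandable as a general term. Section 13.1 places randomisation at week 12, which favours the 2-week figure. Phase II still needs its own origin.

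A reader might also infer that the clock starts at the first enzalutamide dose, 12 to 14 weeks earlier. The documents do not support this: Section 7.1 sets study entry at the first on-study treatment, though it does not tie that date to PFS.

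**Conclusion.** The point holds as a conflict of wording in a secondary endpoint, and it is minor. The death clause has the largest potential effect, but only if 13.3 is applied literally: about 4 to 15 of about 73 events, under an assumed death share of 5% to 20% and with the primary endpoint's planning values as a stand-in. The last-scan rule alone is small. The origin differs by up to about 2 weeks, or about 4 with earlier randomisation, and never-treated patients are left undefined.

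A reader might infer that hazards are overstated overall. That is true only of the last-scan component, by at most about 1.4% in control and 2.5% in combination. Losing deaths works the other way and, at the assumed shares, outweighs it. A reader might also infer a threat to the main result. The documents do not support that: the primary PSA PFS runs from randomisation and is "defined as the time to PSA progression or death, whichever comes first", and the 84 patients and 70 expected events stand.

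**What to change.** Reconcile 11.4 and 13.3 with one Phase II definition:

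- Time PFS from randomisation, for all randomised patients.
- Count death without prior progression as an event on the date of death.
- Censor event-free patients at the later of the last PSA and the last tumour assessment.
- Keep last-scan censoring for radiographic PFS.
- Let start of treatment remain the origin for Phase I.

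The cost is a change of wording, with no new visits, data or patients. The small downside is that the later PSA date credits some time without a supporting scan. The change should be made before the Phase II data are analysed.
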